5.2. Primary Endpoint(s)

The co-primary endpoints for this study are:

- Monocular distance visual acuity 20/40 or better,
- Contact lens related corneal staining,
- Lens fitting acceptability,
- Absolute rotation
- Stability with blink.

5.2.1. Definition

Monocular Visual Acuity (VA) 20/40 or better

Monocular VA with the study lenses will be assessed using a Snellen distance VA chart at an optical distance of 20 feet throughout the study. Observed monocular VA collected during the planned visits (Visits 1 through 5) will be dichotomized whether VA was '20/40 or better' (refer as 'acceptable VA') or 'worse'. VA of 20/40 with a negative modifier will consider to be worse than 20/40. Each eye/subject will be categorized into two groups such that 'response=1' if an eye had acceptable VA or 'response=0' otherwise.

Lens Fit Acceptance

Lens fit characteristics will be assessed via slit lamp in terms of lens position, movement and tightness. Each lens fit collected at fitting (Visit 1) will be judged as being either 'acceptable' or 'unacceptable' based on the static and dynamic fit characteristic.

Lens Stability with Blink

Rotational stability with blink will be assessed via slit lamp with beam that can be rotated. The stability of the scribe mark rotational position during a series of normal (unforced) blinks will be observed. Observed rotational stability with blink will be dichotomized whether stability was ' \leq 5-degree' or 'worse' at fitting (Visit 1).

Absolute Rotation

Lens rotation will be assessed via slit lamp with beam that can be rotated. The rotational error (assume shortest distance) and direction (base towards the nose or based towards temple) will be calculated. Absolute rotation will be dichotomized such that 'response=1' if absolute rotation was less than equal to 10-degree (refer as 'acceptable rotation') or 'response=0' otherwise upon 15-minute post insertion at fitting (Visit 1).

Contact Lens Related Corneal Staining (CS)

Contact lens related corneal staining will be assessed via slit lamp throughout the study. Corneal staining will be graded using a 5-level scale; 0=no staining, 1=trace, 2=mild, 3=moderate and 4=severe. Observed corneal staining collected during planned and unscheduled visits will be dichotomized whether the corneal staining is 'grade 2 or lower' or 'Grade 3 or higher'.

5.2.2. Analysis Methods

Monocular Visual Acuity (VA) 20/40 or better Analysis

Each eye/subject will be categorized into two groups such that 'response=1' if VA was 20/40 or better (refer as 'acceptable VA') throughout all planned visits or 'response=0' otherwise. The generalized linear mixed model (Liang and Zeger, 1986²), as implemented in the SAS/STAT procedure GLIMMIX⁷, will be

used to assess the overall acceptable VA for each lens type utilizing binomial distribution with logit link function. The model will include lens type as a fixed effect and site, subject and eye nested within subject as random effects. Baseline characteristics such as age and gender may be also included in the model as covariates if appropriate.

The model based proportion of eyes with acceptable VA with its corresponding 95% confidence interval (CI) will be constructed for each lens type from the generalized linear mixed model. Overall acceptable VA will be concluded if the lower limit of the 95% CI is greater than or equal to 0.80 (80%).

Lens Fit Acceptance Analysis

Lens fit acceptance at fitting (Visit 1) will be evaluated by lens type if at least 80% of eyes have acceptable lens fit (response=1) using the generalized linear mixed model (Liang and Zeger, 1986²), as implemented in the SAS/STAT procedure GLIMMIX⁷, with binomial distribution and logit link function. The model will include lens type as a fixed effect and site, subject and eye nested within subject as random effects. Baseline characteristics such as age and gender may be also included in the model as covariates if appropriate.

The model based proportion of eyes with acceptable lens fit with its corresponding 95% CI will be constructed for each lens type from the generalized linear mixed model. Acceptable lens fit will be concluded if the lower limit of the 95% CI is greater than or equal to 0.80 (80%).

Lens Stability with Blink Analysis

Observed rotational stability with blink will be dichotomized such that 'response=1' if stability was less than or equal to 5-degree (refer as 'adequate stability') or 'response=0' otherwise. The dichotomized adequate stability at fitting (Visit 1) will be evaluated by lens type if at least 80% of eyes have adequate stability (response=1). The generalized linear mixed model (Liang and Zeger, 1986²), as implemented in the SAS/STAT procedure GLIMMIX⁷, will be used to assess adequate stability for each lens type separately utilizing binomial distribution with logit link function. The model will include lens type as a fixed effects and site, subject and eye nested within subject as random effects. Baseline characteristics such as age and gender may be also included as covariates in the model if appropriate.

The model based proportion of eyes with adequate stability with its corresponding 95% CI will be constructed for each lens type from the generalized linear mixed model. Adequate stability will be concluded if the lower limit of the 95% CI is greater than or equal to 0.80 (80%).

Absolute Rotation Analysis

Acceptable absolute rotation upon 15-minute post insertion at fitting (Visit 1) will be evaluated by lens type if at least 80% of eyes have acceptable absolute rotation (response=1) using the generalized linear mixed model (Liang and Zeger, 1986²), as implemented in the SAS/STAT procedure GLIMMIX⁷, with binomial distribution and logit link function. The model will include lens type as a fixed effect; site, subject and eye nested within subject will be considered as random effects. Baseline characteristics such as age and gender may be considered as covariates in the model when appropriate.

The model based proportion of eyes with acceptable absolute rotation with its corresponding 95% confidence interval (CI) will be constructed for each lens type from the generalized linear mixed model. Acceptable absolute rotation will be concluded if the lower limit of the 95% CI is greater than or equal to 0.80 (80%).

Contact Lens Related Corneal Staining (CS) Analysis

Each eye/subject will be categorized into two groups such that 'response=1' if an eye had acceptable corneal staining (CS) (i.e., CS grade 2 or lower) throughout all planned and unscheduled visits or 'response=0' otherwise. The incidence rate of the Atlas A lens will be compared to the AOA lens using a generalized linear mixed model (Liang and Zeger, 1986²), as implemented in the SAS/STAT procedure GLIMMIX⁷, with binomial distribution and logit link function. The model will include lens type as a

fixed effect and site, subject and eyes nested within subject as random effects. Baseline characteristics such as age and gender may be considered as covariates in the model when appropriate.

The incidence rate of CS for the Atlas A lens will be compared to the AOA lens using the two-sided 95% CI constructed for odds ratios (Atlas A over AOA). No difference between the Atlas A and AOA lenses will be concluded if the 95% CI of the odds ratio contains 1.

In case a full model does not converge for any reasons (likely due to small incidence rate) for any of the primary analyses, a reduced model will be considered.

Additional post-hoc analysis may be conducted if necessary at the discretion of the project leader.

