1.4. Statistical Hypotheses for Study Objectives

1.4.1. Primary Hypotheses

The co-primary endpoints for this study are:

- Monocular distance visual acuity 20/40 or better,
- Lens fitting acceptability,
- Stability with blink,
- Absolute rotation, and
- Contact lens related corneal staining.

Monocular Visual Acuity (VA) 20/40 or better

The proportion of dichotomized monocular VA 20/40 or better in the Atlas A group will be compared to a historical control proportion (p_0) of 80%. The alternative hypothesis (denoted as H_a) is at least 80% of eyes in the Atlas A group will have monocular visual acuity 20/40 or better throughout all planned visits (Visits 1 through 5) whereas the null hypothesis (denoted as H_0) is less than 80% of eyes in the Atlas A group will have monocular visual acuity 20/40 or better. The following hypothesis testing for proportion will be assessed:

$$H_0: p < p_0 \text{ vs. } H_a: p \geq p_0,$$

where p represents the population proportion and p_0 represents a historical control proportion of 80%.

Lens Fitting Acceptability

The proportion of acceptable lens fit at fitting (Visit 1) in the Atlas A group will be compared to a historical control proportion (p_0) of 80%. The alternative hypothesis is at least 80% of eyes in the Atlas A group will have acceptable lens fit at fitting whereas the null hypothesis is less than 80% of eyes in the Atlas A group will have acceptable lens fit. The following hypothesis testing for proportion will be assessed:

$$H_0: p < p_0 \text{ vs. } H_a: p \geq p_0,$$

where p represents the population proportion and p_0 represents a historical control proportion of 80%.

Stability with Blink

The proportion of dichotomized adequate lens stability with blink (adequate stability is defined as lens stability with blink \leq 5-degree) at fitting (Visit 1) in the Atlas A group will be compared to a historical control proportion (p_0) of 80%. The alternative hypothesis is at least 80% of eyes in the Atlas A group will have adequate lens stability with blink at fitting whereas the null hypothesis is less than 80% of eyes in the Atlas A group will have adequate lens stability with blink. The following hypothesis testing for proportion will be assessed:

$$H_0: p < p_0 \text{ vs. } H_a: p \geq p_0,$$

where p represents the population proportion and p_0 represents a historical control proportion of 80%.

Absolute Rotation

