1.5. Sample Size Justification

Sample size was calculated to attain the optimal number of subjects to demonstrate the statistical acceptance of the primary and secondary hypotheses using the historical data from CR5699 and CR5799. The incidence rates (%) of the primary endpoints from the historical data are presented in Table 2 below.

Table 2: Incidence Rate (%) from the Historical Data

Endpoints	Event	Atlas A Rate (%)	AOA Rate (%)
Monocular Visual Acuity 20/40 or better	Overall	100	100
Monocular Visual Acuity 20/20 or better	Overall	93.2	92.9
Corneal Staining < Grade 3*	Overall	100	100
Acceptable Lens Fit	Fitting	100	100
Absolute Rotation within 10-degree	15-min	97	96
Stability with Blink within 5-degree	Fitting	100	100

*Corneal staining will be assessed to demonstrate no difference between the Atlas A and AOA lenses whereas the other primary endpoints will be assessed to demonstrate satisfying a minimum threshold (80%) of the Atlas A.

Primary Endpoints with a 80% Threshold:

The common reference rate of 95% was selected for the sample size calculation as all applicable primary endpoints are binary in nature. Assuming a correlation of 0.8 between eyes, 2000 trials (replicating 2000 trials) were simulated to attain a sample size with a minimum statistical power of 90%.

Primary Endpoints with No Difference:

The incidence reference rate of 0.005% was selected for the sample size calculation for no difference between two study lenses on corneal staining grade 3 or higher using the formula given by Diggle et al. (2002¹) for cluster binary data. The incidence rate of 0.005% was set considering the 5 previous Atlas studies (both sphere and astigmatism) including CR5417, CR5582, CR5726, CR5699 and CR5799. There were no incidences of corneal staining grade 3 or higher among all 5 studies, hence it was deemed that 0.005% is a reasonable incidence rate. The number of observations per subject (cluster) was set to 2 (2 eyes per subject) and a correlation between eyes within a subject was set to 0.3 to attain a sample size with a minimum statistical power of 80%.

Secondary Endpoint:

Sample size calculation for the overall CLUE comfort was also performed considering the effect size of 5 (Atlas A -AOA) to achieve a minimum statistical power of 90%. The 2000 trials were simulated for the repeated measurements from the multivariate normal distribution at a 5% significance level using the following covariance attained from the historical data:

Test:

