5.1. Analysis Specifications

5.1.1. Level of Significance

All planned primary analyses for this study will be conducted with an overall type I error rate of 5%.

The primary analyses (multiple endpoints) will be performed using the intersection-union principal; all primary hypotheses will be simultaneously evaluated using $\alpha = 0.05$. All primary hypotheses must be met in order to claim the success of the study objectives.

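### The four 80% co-primaries are hypotheses about the population proportion, but the SAP does not average its mixed-model proportion over the random effects, so a lens at or just below 80% can pass too often

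*SAP*

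**What the plan says.** - **Hypothesis (SAP 1.4.1).** For each of the four endpoints the null is that fewer than 80% of Test eyes succeed, "where p represents the population proportion and p_0 represents a historical control proportion of 80" per cent.
- **Model (SAP 5.2.2).** A logit-link mixed model, "as implemented in the SAS/STAT procedure GLIMMIX". For VA 20/40: "The model will include lens type as a fixed effect and site, subject and eye nested within subject as random effects". The other three endpoints use the same structure.
- **Decision rule (SAP 5.2.2).** For VA 20/40, "The model based proportion of eyes with acceptable VA with its corresponding 95% confidence interval (CI) will be constructed for each lens type"; for rotation, "The model based proportion of eyes with acceptable absolute rotation with its corresponding 95% confidence interval (CI) will be constructed for each lens type". Fit and blink stability follow the same pattern. Each endpoint passes if the lower limit of the two-sided 95% interval is at least 0.80.
- **Not stated.** Whether the model-based proportion is averaged over the random effects or taken with them at zero, and which GLIMMIX estimation method is used.
- **Planning (SAP 1.5).** True rate 95%, "Assuming a correlation of 0.8 between eyes", more than 90% power with 90 subjects per arm.
- **Fallback.** If the full model fails to converge, SAP 5.2.2 offers a reduced model without defining it. Protocol 9.1 named an Agresti-Coull interval, but SAP 1.1 says the SAP overrides protocol Section 9.

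**The concern.** With a logit link, the success probability for a subject whose random effects are zero is not the population proportion. Above one half it is always larger, and the gap widens as the two eyes become more alike. If GLIMMIX's back-transformed lens-type estimate is used, which is how such output is normally read, the 80% limit is applied to a larger quantity than the one in the hypothesis.

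The lower limit of a 95% interval should pass a lens sitting exactly at 80% about 2.5% of the time. All four threshold endpoints share this rule, all are required for study success (SAP 5.1.1), and the reported Test and Control percentages would carry the same upward shift.

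**Working it through.** **Inputs.** Threshold 0.80; planning rate 0.95; between-eye correlation ρ = 0.8 (SAP 1.5). The SAP's staining value, 0.3, serves as a lower comparison, with 0.5 and 0.1 added as assumptions. Subjects per arm: 90 (SAP Table 3), 115 completers, 135 randomised. Site and eye-level variances are assumed zero and 1.96 is used for t quantiles.

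**Step 1: the plan's own figure.** For a marginal proportion from n subjects with two eyes, Var = p(1−p)(1+ρ)/(2n). At p = 0.95, ρ = 0.8, n = 90: 0.0475 × 1.8/180 = 0.000475, so SE = 0.0218. On the logit scale, SE = 0.0218/0.0475 = 0.459, and the expected lower limit is 2.944 − 1.96 × 0.459 = 2.045, or 0.885. Simulated power is 99.6% (logit interval) or 99.9% (Wald), consistent with the stated figure of more than 90%. The total also reproduces: 180 × 1.15 = 207.

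**Step 2: population versus zero-random-effect proportion.** For a normal subject intercept, solve for β and σ (Z standard normal):

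- E[expit(β + σZ)] = p
- E[expit(β + σZ)²] = p² + ρp(1−p)

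At p = 0.80 the second target is 0.64 + 0.16ρ.

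| ρ | P(both eyes succeed) | σ | β | expit(β) |
|---|---|---|---|---|
| 0.1 | 0.656 | 0.84 | 1.58 | 0.829 |
| 0.3 | 0.688 | 1.76 | 2.08 | 0.889 |
| 0.5 | 0.720 | 3.01 | 2.93 | 0.950 |
| 0.8 | 0.768 | 8.56 | 7.36 | 0.999 |

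At ρ = 0.8 a population 75% maps to 0.997 and 70% to 0.987.

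**Step 3: pass rates under pseudo-likelihood.** Eye pairs were simulated and a random-intercept logit fitted by restricted pseudo-likelihood, the GLIMMIX-type approach. Pass means expit(β̂ − 1.96 SE) ≥ 0.80. Ranges cover separate sets of runs, one-arm and two-arm, with 115 to 135 per arm.

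| True Test rate | ρ | Pass rate |
|---|---|---|
| 80% | 0.8 | 15-20% (about 11% if non-converged fits count as failures) |
| 80% | 0.5 | 7-11% |
| 80% | 0.3 | 3-8% |
| 80% | 0.1 | about 3% |
| 78% | 0.8 | 5-7% |
| 75% | 0.8 | 1-3% |
| 75% | 0.5 | 0.2% |
| 70% | 0.8 | 0% |

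Pseudo-likelihood pulls the estimate well below the Step 2 value: at a true 80% and ρ = 0.8 the median estimate is about 0.84, not 0.999. That is why the excess stays close to the boundary.

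**Step 4: the same rule under full maximum likelihood.** At a true 80% and ρ = 0.8, 77% passed in one-arm fits with 115 subjects and 94% with 135; two-arm fits passed nearly always. Yet at a true 95% and ρ = 0.8, power was about 5% with 90 subjects (one-arm) and 52 of 79 runs with 135 per arm (two-arm), because the variance estimate and the interval become extreme.

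**Step 5: a marginal proportion with a cluster-robust logit interval.** At a true 80%, ρ = 0.8 and 115 subjects, 2.5% passed (4.5% with a Wald interval); at 75%, 0.1%. Power at 95% with 90 subjects is the 99.6% of Step 1.

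**Step 6: convergence and fallback.** At the planning rate (95%, ρ = 0.8, 90 subjects) only 21% of one-arm pseudo-likelihood fits converged. An Agresti-Coull interval that treats the eyes as independent passed a true-80% lens 7.4% of the time at ρ = 0.8 (115 subjects).

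**Step 7: the eye-level term.** Each eye gives one binary record per endpoint. Within an arm, exchangeable eye pairs supply two free quantities (the rate and the between-eye agreement); mean, subject variance and eye variance make three parameters. Fits that included the eye variance returned essentially zero.

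**The case against.** Several stronger readings are tempting, and the documents do not support them.

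- **That the SAP prescribes the average-subject proportion.** It does not say so. It speaks of a model-based proportion of eyes, and SAP 1.4.1 defines p as a population quantity. The zero-random-effect reading is an inference from how such models are normally reported. What is certain is that the SAP leaves the choice open.
- **That lenses clearly below 80% would pass.** Under pseudo-likelihood a 75% lens passes about 1-3% of the time, which is no material inflation.
- **That almost every 80% lens would pass.** This needs full maximum likelihood, which the SAP neither names nor excludes. SAP 6.2.2 applies Kenward-Roger degrees of freedom to all preceding models where applicable, and the title of the cited reference refers to restricted maximum likelihood. That points towards pseudo-likelihood. Full likelihood also does not simply favour passing, since it loses power at high true rates.
- **That 15-20% is the trial's false-success rate.** It is a per-endpoint rate at the boundary. Success requires all five co-primaries.

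Other points in the plan's favour stand. The correlation of 0.8 is a planning assumption, and at 0.3 or lower the excess is small. Historical Test rates in SAP Table 2 are 100% for three of these endpoints and 97% for rotation, far from 80%. The same rates, however, make non-convergence likely, so the undefined reduced model could decide endpoints. The eye-level term had no numerical effect where it was tried and is a minor matter.

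**Conclusion.** The concern holds in a limited form and should be fixed. The hypothesis is about a population proportion, and the analysis as written does not secure an estimate of it. On the usual back-transform with pseudo-likelihood, the one-sided error for a lens at 80% is about 15-20% at the SAP's own correlation, falling to 3-8% at correlation 0.3, against 2.5%. It is about 5-7% at a true 78% and no longer materially inflated at 75%. Under full likelihood the rule would be unreliable in both directions.

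This rests on the inferred reading of the model-based proportion, a normal subject intercept, zero site and eye variances, and a reimplementation of pseudo-likelihood rather than SAS itself. Monte Carlo error is about 1 to 2.5 points for most simulated mixed-model figures. Given the historical rates, the likelier practical problem is non-convergence followed by an unspecified analysis, rather than a poor lens being passed.

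**What to change.** For the four threshold endpoints:

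1. State that the estimand is the marginal (population-averaged) proportion of Test eyes.
2. Estimate it with a logistic GEE or other marginal model: lens type as factor, subject as cluster, exchangeable working correlation, and a cluster-robust 95% interval formed on the logit scale and compared with 0.80. Alternatively, keep the mixed model, name its estimation method, and integrate over the random effects before the comparison.
3. Remove the eye-within-subject term.
4. Replace the undefined reduced model with a named fallback that targets the same proportion and allows for clustering. It must also work when no eye fails, because a robust standard error is then zero. One option is an exact interval on an effective number of eyes, 2n/(1+ρ), with ρ set to 1 when it cannot be estimated. With 115 subjects and no failures the lower limit is 0.025^(1/115) = 0.968. Restoring the protocol's Agresti-Coull interval with eyes treated as independent would not be enough.

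The cost is SAP wording and a different procedure call. Reported percentages become slightly less favourable, and planned power and sample size for these endpoints are unaffected.

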Subjective CLUE comfort and handling score will be assessed using the Contact Lens User ExperienceTM (CLUE) questionnaire. CLUE is a validated patient-reported outcomes (PRO) questionnaire to assess patient-experience attributes of soft contact lenses (comfort, vision, handling, and packaging) in a contact-lens wearing population in the US, ages 18-65. Derived CLUE scores using Item Response Theory (IRT) follow a normal distribution with a population average score of 60 (SD 20), where higher scores indicate a more favorable/positive response. A 5 point increase in an average CLUE score translates into 10% shift in the distribution of scores for population of soft disposable contact lens wearers.

The following primary and secondary hypotheses will be tested throughout the study using a gate keeping strategy. The secondary hypotheses will be tested only if all primary hypotheses are met. Otherwise, no secondary hypotheses testing will be performed.

Primary Study Hypotheses	
1	At least 80% of eyes in the Test group will have monocular visual acuity of 20/40 or better throughout the wear period.
2	The incidence rate of observing contact lens related corneal staining grade 3 or higher for the Test lens will be no different or better than that of the Control lens throughout the wear period.
3	At least 80% of lens fits in the Test group will have acceptable fit at fitting.
4	At least 80% of lens fits in the Test group will have absolute rotation \leq 10 degrees upon 15 minutes post insertion at fitting..
5	At least 80% of lens fits in the Test group will have rotational stability with blink \leq 5 degrees at fitting.
Secondary Study Hypotheses	
1	The proportion of eyes with visual acuity 20/20 or better in the Test group will be non-inferior to that of the Control group at fitting (a non-inferiority margin of 10% will be used).
2	The overall CLUE comfort score assessed throughout the study for the Test lens will be non-inferior to that of the Control lens. A non-inferiority margin of -5 will be used.
3	The overall CLUE handling score assessed throughout the study for the Test lens will be superior to 50 CLUE handling score.

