The model based proportion of eyes with acceptable absolute rotation with its corresponding 95% confidence interval (CI) will be constructed for each lens type from the generalized linear mixed model. Acceptable absolute rotation will be concluded if the lower limit of the 95% CI is greater than or equal to 0.80 (80%).

Contact Lens Related Corneal Staining (CS) Analysis:

Each eye/subject will be categorized into two groups such that ‘response=1’ if an eye had acceptable corneal staining (CS) (i.e., CS grade 2 or lower) throughout all planned and unscheduled visits or ‘response=0’ otherwise. The incidence rate of the Test lens will be compared to the Control lens using a generalized linear mixed model with binomial distribution and logit link function. The model will include lens type as a fixed effect and site, subject and eyes nested within subject as random effects. Baseline characteristics such as age and gender may be considered as covariates in the model when appropriate.

The incidence rate of CS for the Test lens will be compared to the Control lens using the two-sided 95% CI constructed for odds ratios (Test over Control). No difference between Test and Control lenses will be concluded if the 95% CI of the odds ratio contains 1.

Monocular Visual Acuity (VA) 20/20 or better Analysis:

Observed monocular VA will be also dichotomized such that ‘response=1’ if VA was 20/20 or better (refer as ‘suitableVA’) or ‘response=0’ otherwise at fitting. Dichotomized VA at fitting will be compared between the Test and Control lenses using a generalized linear mixed model with binomial distribution and logit link function. The

model will include lens type as a fixed effect and site, subject and eyes nested within subject as random effects. Baseline characteristics such as age and gender may be considered as covariates in the model when appropriate.

The model based proportion of eyes with suitable VA at fitting will be compared between the Test and Control lenses using the two-sided 95% CI constructed for odds ratios (Test over Control). Non-inferiority will be concluded if the lower limit of the two-sided 95% CI of the odds ratio is above 0.4. The odds ratio margin of 0.4 corresponds to a 10% difference in proportion between the Test and Control lenses assuming a reference rate of 93%.

CLUE Score Analysis:

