The proportion of dichotomized acceptable absolute rotation (acceptable absolute rotation is defined as absolute rotation \leq 10-degree) at 15-minute post insertion (Visit 1) in the Atlas A group will be compared to a historical control proportion (p_0) of 80%. The alternative hypothesis is at least 80% of eyes in the Atlas A group will have acceptable absolute rotation at 15-minute post insertion whereas the null

hypothesis is less than 80% of eyes in the Atlas A group will have acceptable absolute rotation. The following hypothesis testing for proportion will be assessed:

$$H_0: p < p_0 \text{ vs. } H_a: p \geq p_0,$$

where p represents the population proportion and p_0 represents a historical control proportion of 80%.

Contact Lens Related Corneal Staining (CS)

The proportion of dichotomized unacceptable contact lens related CS (unacceptable CS is defined as CS grade 3 or higher) in the Atlas A group will be compared to the proportion of that in the AOA group throughout all planned and unplanned visits. The alternative hypothesis is the odds of unacceptable CS incidence rate in the Atlas A group ($OR_{Atlas A}$) is not statistically different from the odds of that in the AOA group (OR_{AOA}) throughout the wear period. The following hypothesis testing for odds ratio will be assessed:

$$H_0: OR = 1 \text{ vs. } H_a: OR \neq 1,$$

where OR represents the ratio of $OR_{Atlas A}$ over OR_{AOA} ($OR_{Atlas A}/OR_{AOA}$) and Ψ_0 represents a margin of 1 that reflects distribution similarity between the Atlas A and AOA groups.

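### The corneal staining model codes the opposite outcome from the one on which SAP 1.4.1 defines the odds ratio, and its undirected rule does not match the Protocol 4.1 hypothesis, which also accepts a better Test lens

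*SAP*

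**What the plan says.** **Hypotheses.** Protocol 4.1, primary hypothesis 2, is that the rate of grade 3 or higher staining with the Test lens "will be no different or better than that of the Control lens throughout the wear period". SAP 1.4.1 frames the comparison as an odds ratio, Atlas A over AOA, on "the odds of unacceptable CS incidence rate in the Atlas A group", where unacceptable means grade 3 or higher. Its prose alternative is that these odds are such that the Test group "is not statistically different from the odds of that in the AOA group". The formula beneath reads H0: OR = 1 against Ha: OR ≠ 1.

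**Model.** SAP 5.2.2 assigns response=1 "if an eye had acceptable corneal staining (CS) (i.e., CS grade 2 or lower" at every planned and unscheduled visit, and 0 otherwise. It then describes the compared quantity as an incidence rate of staining and judges it "using the two-sided 95% CI constructed for odds ratios (Atlas A over AOA"). Protocol 9.1 uses the same coding. Neither document names the level modelled as the event.

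**Decision.** SAP 5.2.2: "No difference between the Atlas A and AOA lenses will be concluded if the 95% CI of the odds ratio contains 1". Protocol 9.1: "No difference between Test and Control lenses will be concluded if the 95% CI of the odds ratio contains 1". Neither says what follows if the interval excludes 1 in favour of Test.

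**Consequences.** SAP 5.1.1 requires all primary hypotheses to be met, and SAP 6.1.1 opens the secondary analyses only in that case. SAP 1.1 lets the SAP override Protocol Section 9. The Protocol 4.1 hypothesis lies outside that clause.

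**The concern.** Two things do not line up.

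1. *Event.* The odds ratio is defined on unacceptable staining, but the variable handed to the model is acceptable staining. With the lens order unchanged, modelling response=1 gives a ratio that exceeds 1 when Test is better, the opposite of the definition. A reader of a safety result would take the direction wrongly.
2. *Direction.* The hypothesis in Protocol 4.1 is one-directional: equal or better is success. The rule is undirected. Read literally, an interval wholly in favour of Test does not give the only conclusion the rule offers, so a co-primary is not met, and with it the study objective and access to the secondary tests.

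The two interact. If a directional rule is written in without changing the coding, it will judge the wrong side.

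**Working it through.** **The plan's own figure.** SAP Table 3 gives 116 subjects per arm and more than 85% power for staining. It cannot be rebuilt from stated inputs, because only one rate (0.005%) is given and no difference to detect. Taking the two-sided two-proportion formula multiplied by 1.3/2 for clustering, and *assuming* second rates of 2%, 3%, 4% and 5%, power at 116 per arm is 47.3%, 64.4%, 77.1% and 85.9%. Only the 5% assumption fits. Nothing below depends on that figure.

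**Inputs.** Eyes per arm: 115 completers × 2 = 230 (SAP 1.3). Between-eye correlation: 0.3, with 2 eyes per subject (SAP 1.5). Planning rate: 0.005% (SAP 1.5).

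**Step 1: which level is the event?** For the four endpoints with an 80% threshold, SAP 5.2.2 requires the proportion with the favourable outcome to reach 80%. For 20/20 acuity, SAP 6.2.2 concludes non-inferiority when the *lower* odds-ratio limit exceeds its margin, which makes sense only if response=1 is the event. Consistent reading therefore makes acceptable staining the event. The text never says so for staining.

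**Step 2: effect of the coding.** Swapping event and non-event turns (OR, L, U) into (1/OR, 1/U, 1/L).

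Design effect = 1 + (2 − 1) × 0.3 = 1.3. For *a* Test and *c* Control events:

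- OR = [a/(230 − a)] / [c/(230 − c)]
- SE = √{1.3 × [1/a + 1/(230 − a) + 1/c + 1/(230 − c)]}
- 95% CI = exp(ln OR ± 1.96 × SE)

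For 4 v 2 events: OR = (4/226)/(2/228) = 2.02. The bracket is 1/4 + 1/226 + 1/2 + 1/228 = 0.7588, so SE = √(1.3 × 0.7588) = 0.993 and the CI is 0.29 to 14.1. As coded, the output would be 0.50 (0.07 to 3.47). Both intervals contain 1, so the verdict is the same. The first reads as twice the odds of staining, the second as half.

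**Step 3: when does a better Test lens miss the rule?**

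| Test v Control events | OR (unacceptable) | 95% CI, design effect 1.3 | Contains 1? |
|---|---|---|---|
| 1 v 8 | 0.121 | 0.011 to 1.31 | yes |
| 1 v 10 | 0.096 | 0.009 to 1.01 | yes |
| 1 v 11 | 0.087 | 0.008 to 0.906 | no |

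With eyes treated as independent, 1 v 8 would exclude 1 (0.015 to 0.977), but the plan's own correlation removes that. With 270 eyes per arm (135 × 2, the most the safety set could hold if all 270 are fitted), the upper limits for 1 v 10 and 1 v 11 are 1.02 and 0.911, so the threshold does not move.

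**Step 4: how likely is that?** Expected events at the planning rate: 460 × 0.00005 = 0.023 in both arms together. Twelve events is about 12/0.023 ≈ 520 times that. With independent eyes, the chance of no event at all is 0.99995^460 ≈ 0.977, and 0.99995^540 ≈ 0.973 for 540 eyes.

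A second approximation uses Fisher's exact test at an effective 135 × 2/1.3 ≈ 208 eyes per arm. The probability that the interval excludes 1 in favour of Test is effectively 0 at 0.005% in both arms, and about 0.0002 at 0.5% in both. It becomes material only at assumed rates far from the plan's: with Test 0% and Control 2%, the undirected rule passes 76.1% of the time and a directed rule 100%.

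**Step 5: check of the directed rule.** With grade 3 or higher as the event, and not met only if L > 1: 1 v 11 gives U = 0.906, met; 4 v 2 contains 1, met; 11 v 1 gives 11.5 (1.10 to 119.8), not met. Applied to the reciprocal, the results for 1 v 11 and 11 v 1 swap.

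**The case against.** The best reply has three parts.

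*The inversion is not established.* SAP 5.2.2 speaks of an incidence rate of staining and expects non-convergence from a small incidence rate. That fits grade 3 or higher, not an acceptable rate near 100%. This stands as far as it goes: the documents support an unnamed event level whose consistent reading is the reciprocal, not certain inversion. A reader might infer that the coding makes the trial reach the wrong decision. It cannot under the current rule, because containing 1 is unaffected by inversion.

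*The undirected rule matches the SAP.* SAP 1.4.1 and the footnote to SAP Table 2 speak of no difference, and the words about a better lens are in Protocol 4.1 only. This is right, and it makes the point a conflict between the documents. It does not remove it, since SAP 1.1 overrides Protocol Section 9 and not Section 4.1.

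*A better lens will not fail in practice.* A reader might infer that a clearly better Test lens stands a real chance of sinking the study. The plan's own inputs do not support that: five earlier studies had no such event, and a split as lopsided as 1 v 8 still contains 1 once the 0.3 correlation is applied. Nor does either document state that an interval wholly favouring Test is a failure. It simply has no conclusion assigned to it.

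**Conclusion.** The point holds as a specification fault with little practical risk. The modelled response and the defined odds ratio refer to opposite outcomes. If response=1 is the event, the reported estimate and interval are reciprocals of those in SAP 1.4.1, with no effect on pass or fail. The rule also lacks the direction that Protocol 4.1 gives the hypothesis, and the formal H0 and Ha in SAP 1.4.1 place equality in the null although the prose makes it the claim.

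For the missing direction to matter, Test would have to be significantly better: about 1 v 11 events with 230 eyes per arm. This rests on Wald intervals inflated by a design effect of 1.3, which only approximate the planned mixed model, and the likelihood statement rests on the 0.005% planning rate. The repair is worthwhile because the endpoint is a co-primary safety comparison that gates everything else.

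**What to change.** - **SAP 5.2.2:** name grade 3 or higher at any planned or unscheduled visit as the modelled event, so that an odds ratio above 1 means Test is worse, as SAP 1.4.1 defines it.
- **SAP 1.4.1:** align the prose with Protocol 4.1, and restate H0 and Ha so that they agree with it.
- **Decision rule:** the hypothesis is not met only if the whole two-sided 95% interval lies above 1 (lower limit above 1). An interval wholly below 1 counts as met.

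The recoding and the directed rule must go in together (Step 5 above).

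The rule should not be written on the upper limit without a threshold. Set against 1, the upper limit would demand superiority, which is stricter than Protocol 4.1. A non-inferiority rule on the upper limit needs a pre-specified, justified margin, and the documents give none. The margin-free repair has a limit of its own: in the Fisher approximation at 208 effective eyes per arm, a Test lens at an assumed 2% against 0.5% passes about 89% of the time under either rule. It settles direction and does not demonstrate similarity.

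Cost: a few sentences in SAP 1.4.1 and 5.2.2 and one line of code naming the event level, made before unmasking, with no change to data collection. Choosing a margin instead would cost more, since it would have to be justified and the sample size rechecked.
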